A literature review was performed that searched for randomized clinical trials involving ketamine IV boluses for acute pain in the Emergency Department. Studies involving continuous infusions or intranasal routes of ketamine administration were not included. Thirteen randomized clinical trials were identified meeting this criteria.^{9-11, 14-23} None of these trials directly compared ketamine doses within the 0.1-0.3 mg/kg range for pain score reduction and adverse events. Many of these trials concluded with the recommendation that further studies were needed to evaluate the optimal dosing of ketamine for acute pain and determine which populations are most ideal for its use. This study will be the first to evaluate ketamine for acute pain in the emergency department at standard of care doses (0.1 mg/kg, 0.2 mg/kg, and 0.3 mg/kg IV) to determine which dose correlates with the most efficacy and safety.

III. Drug Information

Ketamine is a dissociative anesthetic with amnestic properties that is used for analgesia at low doses. It works primarily through *N*-methyl-D-aspartate receptor antagonism, with a lesser degree of effect on nicotinic, opioid, muscarinic, and dopaminergic receptors. It has an onset of

action of 30 seconds with a variable duration for analgesic effect, ranging from 2-4 hours. Ketamine is primarily metabolized in the liver and eliminated by the kidneys. The half-life of ketamine is variable, with an average of 2.5 hours reported in the literature. Side effects associated with ketamine are fatigue, dizziness, nausea, headache, feelings of unreality, changes in hearing, changes in vision, mood change, generalized discomfort, and hallucination.²⁴

IV. Inclusion Criteria

Patients will be included if they present to the Adult Emergency Department with (all of the following):

- Acute pain (including acute or chronic pain)
- Pain score of moderate to severe ($\geq 4/10$) on the Numerical Rating Scale
- Provider determines the patient requires intravenous ketamine for analgesia

V. Exclusion Criteria

Patients will be excluded from the study based on our existing ketamine for acute pain management in the emergency department guideline at Hackensack University Medical Center (Appendix B).

- History of hypersensitivity to ketamine
- Altered mental status
- Psychiatric illness
- Known history of renal or hepatic insufficiency
- Acute head or eye injury
- Suspected intracranial hypertension or mass
- Headache as the chief complaint

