- Alcohol or drug abuse
- Received an analgesic within the last four hours
- History of congestive heart failure
- History of aortic or brain aneurysm
- Active Chest Pain
- Porphyria
- Active methadone treatment
- Pregnant or breastfeeding
- Signs of respiratory, hemodynamic, or neurologic compromise
 - Systolic blood pressure < 90 mmHg or > 180 mmHg
 - Heart rate < 50 beats per minute or > 150 beats per minute
 - Respiratory rate < 10 breaths per minute or > 30 breaths per minute
 - Glasgow Coma Score < 15
- Previously received ketamine ≤ 0.3 mg/kg IV for acute pain in the emergency department

VI. Recruitment Procedures

This is a single-center, prospective, randomized, double-blind, active controlled trial that will identify patients in the emergency department with acute pain who meet the eligibility criteria from January 2019 through January 2021 to achieve a sample of at least 180 patients.

VII. Definitions

Adequate pain relief:

- A score decrease on the Numerical Rating Scale (NRS) by ≥ 3 points

Moderate pain:

- A NRS score of 4-7 out of 10 per hospital policy

Severe pain:

- A NRS score of 8-10 out of 10 per hospital policy

Rescue analgesia:

- Any IV analgesic to be determined by the treating provider

Opioid tolerant:²⁵

- Patients receiving, for one week or longer, at least 60 mg oral morphine/day, 25 mcg transdermal fentanyl/hour, 30 mg oral oxycodone/day, 8 mg oral hydromorphone/day, 25 mg oral oxymorphone/day, or an equianalgesic dose of another opioid

VIII. Methodology

This is a single-center, prospective, randomized, double-blind, active-controlled trial. Patients who meet inclusion criteria and none of the exclusion criteria will be enrolled from January 2019 to January 2021 to achieve a goal sample size of 180 patients. Data such as demographics, self-reported pain score, adverse drug events, vital signs, and need for rescue analgesia within two hours of ketamine administration will be reported. Outcomes will include pain score reduction, incidence and severity of adverse drug events, adequate pain relief, and need for rescue analgesia within two hours of ketamine administration. All data will be entered in a password protected data sheet for proper analysis. No patient identifying data will be recorded.

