25. Food and Drug Administration (FDA). Extended-release (ER) and long-acting (LA) opioid analgesics Risk Evaluation and Mitigation Strategy (REMS). www.fda.gov/downloads/drugs/drugsafety/postmarketdrugsafetyinformationforpatientsandproviders/ucm311290.pdf. Accessed September 20th, 2018.

XVIII. Appendix A

Demographics				
Subject #:	Date/Time:		Age:	Sex: Male / Female
Opioid Tolerant?*:  Yes  No	Weight (kg):	SBP:	HR:	RR:
Initial Pain Score Immediately Prior to Randomization (0-10):				

*Opioid tolerant: Patients receiving, for one week or longer, at least 60 mg oral morphine/day, 25 mcg transdermal fentanyl/hour, 30 mg oral oxycodone/day, 8 mg oral hydromorphone/day, 25 mg oral oxymorphone/day, or an equianalgesic dose of another opioid
				
Eligibility				

If the subject does not meet all of the eligibility criteria, do not proceed with randomization.
				

Inclusion Criteria (if any answer is “no”, stop immediately):
				

1) Acute pain (including acute or chronic)?
 
Type of Pain (Circle)
 
Abdominal
 
Flank
 
Back
 
Musculoskeletal
 
Complex Regional Pain Syndrome
 
Neuropathic
 
Radicular
 
Sickle Cell
 
Trauma
 
Other _____
				

2) NRS pain score $\geq 4/10$?
 
3) Provider determines the patient requires intravenous ketamine?
				

Exclusion Criteria (if any answer is “yes”, stop immediately):
				

1) History of hypersensitivity to ketamine?
 
2) Altered mental status?
 
3) Pregnant or breastfeeding?
 
4) Psychiatric Illness?
 
5) Known history of renal or hepatic insufficiency?
 
6) Acute head or eye injury?
 
7) Suspected intracranial hypertension or mass?
 
8) Headache as the chief complaint?
 
9) Alcohol or drug abuse?
 
10) Received an analgesic within the last 4 hours?
 
11) History of congestive heart failure?
 
12) History of aortic or brain aneurysm?
 
13) Active chest pain?
 
14) History of porphyria?
 
15) Active methadone treatment?
				

16) Signs of respiratory, hemodynamic, or neurologic compromise?

Defined as SBP < 90 mmHg or > 180 mmHg, HR < 50 or > 150, RR < 10 or > 30, or GCS < 15.

17) Previously received ketamine \leq 0.3 mg/kg IV for acute pain in the emergency department

I have reviewed all of the inclusion and exclusion criteria and the patient is a candidate for this study: Yes No

Treatment

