CONTRAINDICATIONS

 • Hypersensitivity to ketamine • SBP > 180 and DBP > 100 mmHg • HR < 50 or > 150 bpm • Elevated intracranial pressure • Increased intraocular pressure • Pregnant or breastfeeding • Acute head or eye injury 	
 • Congestive heart failure - stage III and IV (myocardial depressant effects) • Aneurysm • Angina • Psychiatric disorders • Porphyria • Active methadone treatment
---	---

RELATIVE CONTRAINDICATIONS

- SBP <90 or > 140 mmHg
- Renal or hepatic insufficiency
- Alcohol or drug abuse
- Coronary artery disease

PRECAUTIONS

- Emergence reactions (vivid dreams, hallucinations, frank delirium, confusion, excitement, or irrational behavior) are dose-related but may occur at the subanesthetic doses used for treatment of acute pain
- Patients > 65 years old

DOSAGE AND ADMINISTRATION

1. Dosages:

- Single dose of 0.1 – 0.3 mg/kg/dose (maximum single dose: 30mg) administered over 20 minutes via intermittent infusion
 - Lower doses should be initiated for elderly patients or those with renal/hepatic dysfunction
 - Doses greater than 0.3 mg/kg/dose may lead to dissociative effects
- Dose may be repeated after 60 minutes up to a total cumulative dose of 0.3mg/kg or 30mg
- An additional dose may be repeated after 4 hours for patients requiring ongoing analgesia while remaining in the ED

2. Standard Dilution: Weight based dose diluted into 100 mL D5W or NS

TREATMENT OF EMERGENCE REACTION

- Emergence reaction may be treated with short acting benzodiazepines
- Midazolam 1mg IV once (0.5mg IV in the elderly) administered by the provider is typically sufficient
 - Doses may be repeated if necessary

DRUG INTERACTIONS

Ketamine is a substrate for CYP2B6, CYP2C9, & CYP3A4. The following includes, but is not limited to a list of drugs that may increase the levels/effects of ketamine.

- Sertraline, paroxetine (2B6)
- Fluconazole, nicardipine, NSAIDs, sulfonamides (2C9)
- Azole antifungals, clarithromycin, propofol, nicardipine (3A4)

ADVERSE REACTIONS

● Hypertension● Tachycardia/bradycardia● Tonic/clonic movements, tremor● Increased intracranial pressure● Emergence reaction/ dissociative effects (vivid dreams, hallucinations, frank delirium, confusion, excitement, or irrational behavior)	
● Visual disturbances (diplopia and nystagmus)● Nausea, vomiting● Skin rash● Headache● Fatigue
--	--

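### Increased intraocular pressure is a contraindication in the guideline behind the exclusions, but neither section V nor the Appendix A checklist asks about it

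*Combined protocol and SAP*

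**What the plan says.** Section V (Exclusion Criteria) opens by naming its source: "Patients will be excluded from the study based on our existing ketamine for acute pain management in the emergency department guideline". It points to Appendix B and then gives a bulleted list.

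Appendix B separates contraindications from relative contraindications. Under the first heading it has "Increased intraocular pressure" and, as a different entry, "Acute head or eye injury".

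Section VIII (Methodology) makes the section V list operative: "Patients who meet inclusion criteria and none of the exclusion criteria will be enrolled". The Appendix A data collection form turns that list into 17 yes/no exclusion items. The only one that concerns the eye is "6) Acute head or eye injury". The form instructs the user: "If the subject does not meet all of the eligibility criteria, do not proceed with randomization". It ends with a declaration for the clinician to complete: "I have reviewed all of the inclusion and exclusion criteria and the patient is a candidate for this study".

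**The concern.** An exclusion list that says it rests on a safety guideline should carry that guideline's full contraindications, or explain why one is left out. Here one is missing from both places where a screening clinician would look, and no reason is given.

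What is at stake is participant safety, not inference. Section X calls the study risks minimal because ketamine is already standard of care in this department. That argument does not extend to a patient for whom the same department's guideline lists the drug as contraindicated. The treating clinician is also blinded to which of the three doses the patient receives.

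**Working it through.** No arithmetic applies, so the check sets the three lists side by side and then follows one patient through the form.

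**Step 1. Eye-related and pressure-related entries in the three places.**

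| Condition | Appendix B, contraindications | Section V | Appendix A checklist |
|---|---|---|---|
| Acute injury to head or eye | Own entry | Listed | Item 6 |
| Raised intracranial pressure | Own entry | Listed, as suspected intracranial hypertension or mass | Item 7 |
| Raised intraocular pressure | Own entry | Not listed | No item |

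The three conditions are distinct entries in Appendix B, so the injury item cannot be read as standing in for the pressure item. The intracranial item concerns the skull, not the eye.

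**Step 2. A test patient.** Take an adult with acute pain scoring 4 or more, raised intraocular pressure, no eye or head injury, and nothing else on the list. Items 6 and 7 are answered no, truthfully. By construction, the other 15 items (17 - 2 = 15) are also no, and none of them names an eye condition. Another item might exclude a particular patient by coincidence, for example headache as the main complaint, but no item does so because of the eye pressure. If the provider has judged that intravenous ketamine is required, all three inclusion items are yes. The declaration can then be completed, and nothing on the form stops randomisation.

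**Step 3. Does the list look like a deliberate relaxation?** Elsewhere section V is mostly stricter than its source. Any history of congestive heart failure excludes, where Appendix B names stages III and IV only. Renal or hepatic insufficiency, alcohol or drug abuse, and systolic pressure below 90 mmHg are only relative contraindications in Appendix B but are exclusions in section V. Dropping a full contraindication runs against that pattern. This suggests an oversight in carrying the list over, although the documents do not say so.

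**The case against.** The strongest reply has three parts.

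First, a list based on a guideline need not be identical to it, and the authors were free to adapt it. That is fair in general. It does not explain why a full contraindication was left out while relative ones were promoted.

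Second, the opening sentence of section V can be read as bringing in the whole of Appendix B, so such a patient is already excludable. That reading is available. The form that clears patients still does not put the question, and section VIII ties enrolment to the stated criteria.

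Third, safeguards come before or surround randomisation. A provider must decide that intravenous ketamine is needed, department staff were educated on the guideline, an ED pharmacist places the order, and Appendix B requires direct attending supervision. Randomisation then only selects a dose within the range already in use. This stands as mitigation and is why the gap is minor. It does not close the gap, because the same safeguards cover hypersensitivity, porphyria and methadone treatment, and the checklist still asks about each of those.

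A reader might go further and infer that the carry-over from Appendix B is unsound more widely. The documents do not support that:

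- **Angina.** Section V uses active chest pain instead. That is broader in one direction, since it covers chest pain of any cause. Appendix B places coronary artery disease only among the relative contraindications, so its absence from the checklist is not a discrepancy with the full contraindications.
- **Blood pressure.** Appendix B, read literally, requires systolic pressure above 180 together with diastolic above 100 mmHg. Excluding on systolic pressure alone is stricter than that.
- **Aneurysm.** Appendix B names no site, while section V has "History of aortic or brain aneurysm". The narrower wording is repeated in checklist item 12 and may be deliberate. It merits an optional query at most.

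**Conclusion.** The point holds for increased intraocular pressure alone. It is a full contraindication in the guideline on which the exclusions are said to rest, and it appears in neither the section V list nor the 17-item checklist. The form as written can therefore clear a patient whom the hospital's guideline would not treat with ketamine.

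The gap is small and worth correcting. The number affected among the planned 180 is probably low, but the documents give no prevalence from which to estimate it. The conclusion assumes that clinicians screen from the checklist as printed and do not consult Appendix B separately for each patient. If they do consult it, the practical risk is lower still.

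It should not be inferred that contraindicated patients were in fact enrolled, or that the trial's results are compromised. The documents contain no enrolment data, and the omission does not enter the randomisation, the primary outcome or any test.

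**What to change.** Add increased intraocular pressure (known or suspected) as an exclusion in section V, and add a matching item to the Appendix A checklist. If the authors wish, they can also add a short statement on whether the aortic-or-brain limit on aneurysm is intended.

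The cost is an amendment of one line and one checklist item. A few more patients become ineligible. Sample size and analysis stay as they are.

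One point of timing: the document is dated 4/20/2021, after the January 2021 end of enrolment given in sections VI and VIII, and it does not say whether enrolment has closed. If it has, the change would serve only later work, such as the larger study that section IX has in view.

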**Hackensack University Medical Center
Institutional Review Board**

NCT03896230 Unique Protocol ID: Pro2018-0970

Comparison of ketamine 0.1 mg/kg, 0.2 mg/kg, and 0.3 mg/kg intravenous doses for acute pain in the emergency department: A prospective, randomized, double-blind, active-controlled, clinical trial

**[name], BCPS
Emergency Medicine Clinical Pharmacist
Hackensack University Medical Center**

Study Team:

**[name]
[name], BCCCP
[name]**

Version - 4/20/2021

Table of Contents

I.	Objectives of the Study.....	3
II.	Background Material.....	3-5
III.	Drug Information.....	5-6
IV.	Inclusion Criteria.....	6
V.	Exclusion Criteria.....	6
VI.	Recruitment Procedures.....	6
VII.	Definitions.....	7
VIII.	Methodology.....	7-8
IX.	Statistical Considerations.....	8-10
X.	Discomfort and Risks.....	10
XI.	Benefits.....	10
XII.	Criteria for Evaluating Response.....	10
XIII.	Confidentiality.....	10
XIV.	Credentials, Training.....	11
XV.	Bibliography.....	11-13
XVI.	Appendix A.....	14-15
XVII.	Appendix B.....	16-18

I. Objectives of the Study

Primary Objectives

This study will prospectively compare the mean Numerical Rating Scale (NRS) pain score reduction amongst three recommended dosing strategies of intravenous ketamine (0.1 mg/kg, 0.2 mg/kg, and 0.3mg/kg) for acute pain in the emergency department (ED).

Secondary Objectives

This study will also examine the frequency of adverse events secondary to ketamine including fatigue, dizziness, nausea, headache, feeling of unreality, changes in hearing or vision, mood changes, generalized discomfort, and hallucinations, changes in vital signs. Subgroups for exploratory analysis based on the need for rescue analgesia within two hours of ketamine administration, adequate pain relief, previous opioid tolerance, and age (adults < 65 years old and > 65 years old).

II. Background Material

Pain is one of the most common reasons for presentation to the emergency department, with studies reporting it being responsible for up to 78% of visits. Accordingly, pain reduction is one of the primary goals of emergency medicine.¹ Opioids are among the most common analgesics used to treat pain in the emergency department.² The increasing use of opioids has made treating acute pain difficult due to increased concern for opioid tolerance, abuse, and misuse.³

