Ketamine was studied as an adjunct to morphine in a trial designed to compare effectiveness with morphine alone. Sixty patients were split into three equal groups of morphine 0.1 mg/kg IV push alone (standard care), morphine 0.1 mg/kg IV push plus ketamine 0.15 mg/kg IV push, and morphine 0.1 mg/kg IV push plus ketamine 0.3 mg/kg IV push. Pain scores, need for rescue analgesia, changes in vital signs, and adverse events were collected and analyzed. The primary outcome was pain score reduction, with secondary outcomes measuring pain scores at each time point, patient-perceived analgesia, time and amount of rescue analgesia required, and global analgesic effectiveness. Adverse events were recorded and assessed at baseline and at each time point. The pain-intensity difference (PID) is a measurement of the baseline pain score minus the pain score at the specific time point. While PID was significantly different in the standard care group when compared with both ketamine groups at 30 minutes, it lost significance when compared to the ketamine 0.15mg/kg IV group at 60 and 120 minutes. There were no differences in analgesia between the two ketamine groups at any of the study endpoints. There were no differences in the use or amount of rescue analgesia between any of the groups, but the standard care group did require rescue analgesia sooner. While the study was not powered to detect a difference in the frequency of adverse events, no serious adverse events were noted. Dizziness was reported more in the ketamine 0.3 mg/kg IV group when compared with either group. The authors conclude that ketamine 0.3 mg/kg IV may be more efficacious than ketamine 0.15 mg/kg IV when used as an adjunct to morphine for acute pain in the emergency department.¹⁰ This discrepancy in the analgesic effect of two recommended doses of ketamine warrants further investigation.

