Motov and colleagues performed one of the first head to head studies of ketamine alone and morphine alone for pain in the emergency department in 2015. In this prospective, double-blind, single center trial, 90 participants were randomized to either ketamine 0.3 mg/kg IV push or morphine 0.1 mg/kg IV push. The primary outcome was a comparative reduction in pain scores at 30 minutes after medication administration, need for rescue analgesia, vital sign changes, and adverse effects also collected. All patients reported reductions in their pain scores at 15 and 30 minutes, with no statistically significant differences between the two groups. At the primary outcome of 30 minutes, the mean difference in pain score between the ketamine and morphine group was 0.2 (95% CI -1.19 to 1.46; p = 0.97). There was no significant difference in the need for rescue analgesia between the two groups until 120 minutes, where the ketamine group did require more rescue fentanyl (percentage difference 17%, 95% CI 1% to 34%). There were no serious adverse events in either group or clinical concerning changes in vital signs. No adverse events required treatment in either group. However, ketamine patients reported a statistically significant increase in the number of adverse events immediately after medication administration and at 15 minutes (percentage difference 38%, 95% CI 18% to 57%). The authors conclude that ketamine 0.3 mg/kg IV provides analgesic efficacy and safety comparable to morphine for acute pain in the emergency department.¹¹

In order to investigate the analgesic effect and safety of ketamine in the geriatric population, Motov and colleagues performed a prospective, randomized, double-blind trial comparing ketamine to morphine. They enrolled sixty patients aged 65 and older and randomized them

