The administration of ketamine 0.1 – 0.3 mg/kg IV for acute pain in the Adult Emergency Department was approved at the September 2018 Pharmacy and Therapeutics Committee and is currently standard of care. Education was provided to all providers and nurses in the emergency department.

Patient screening, enrollment, and data collection will be performed by the treating resident or attending who will remain blinded. The Primary Investigator will also remain blinded and the ED pharmacists will be unblinded to facilitate ordering and delivery of the study drug.

Patients who consent to the study and meet eligibility criteria will be randomized to one of three doses of ketamine (0.1 mg/kg, 0.2 mg/kg, or 0.3 mg/kg) to be given IV infusion over 20 minutes. The block randomization list will be generated by the Hackensack Meridian Health Biostatistician prior to patient enrollment. Pharmacy investigators will maintain the randomization list and deliver the medication to the nurse in a blinded fashion. The medication will be prepared as a 0.1 mg/kg, 0.2 mg/kg, or 0.3 mg/kg dose in a 100 mL solution of dextrose 5% or sodium chloride 0.9% according to the predetermined randomization list. If there is a significant delay from the initial pain score to the study dose of ketamine administration, the patient will be withdrawn from the study and receive standard of care treatment. If pain is not controlled after the administration of ketamine, providers can order a rescue analgesic of their choice.

Patient history will be reviewed for known allergies, resuscitative equipment will be readily available, and the type and intensity of pain prior to administration will be documented. Baseline

vital signs, such as blood pressure, heart rate, and respiratory rate, will be assessed prior to IV administration of ketamine and at 120 minutes after infusion or upon discharge, whichever is sooner. The patient's self-reported pain score, need for rescue analgesia, and any adverse drug effects will be reassessed within 15 minutes from the end of the infusion and then every 30 minutes for up to 120 minutes or until discharge, whichever is sooner. Incidence, severity, and total number of adverse drug events will be documented using the Side Effects Rating Scale for Dissociative Anesthetics (SERSDA).

Procedure:

- Patient consent, screening, and enrollment will be performed by the treating resident or attending who will remain blinded
- Patient will be assigned a subject number

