- Treating resident or attending will notify the ED pharmacist that a patient has been enrolled in the trial
- ED pharmacist will notify the IV room and place the study drug order
- Either the ED pharmacist or a pharmacy supervisor will randomize the subject based on the predetermined randomization list
- Study drug will be prepared as 0.1 mg/kg, 0.2 mg/kg, or 0.3 mg/kg IV dose in a 100 mL solution of dextrose 5% or sodium chloride 0.9%
- ED pharmacist will promptly deliver the study drug to the ED
- Baseline vital signs will be assessed prior to starting the study drug infusion
- Study drug will be administered via IV infusion over 20 minutes
- Treating resident or attending will reassess the patient at 15 minutes from the end of infusion, at 30 minutes from the end of infusion, and then every 30 minutes for up to 120 minutes or until discharge, whichever is sooner

IX. Statistical Considerations

Randomization

The study participants will be randomly assigned into one of the three dose groups in the ratios of 1:1:1. Block randomization will be used to balance the sample size in each group.

Primary Outcome

The primary outcome is the numerical rating scale (NRS) pain score reduction from baseline to 120 minutes after the injection. The null hypothesis is that there is no difference among those three doses with respect to the mean score reduction.

Describing Data

The continuous variables (such as age of participant at the time of study) will be summarized using mean, median, standard deviation, interquartile range, range, minimum and maximum. The discrete variables (such as sex) will be summarized using frequency and percentage.

Exploring Differences

The two-sample Student's t-test will be used to compare the continuous variables between groups. If the normality assumption is violated, the Wilcoxon rank sum test will be used. The Shapiro-Wilk test will be used to evaluate the normality. The one-way analysis of variance (ANOVA) will be used to compare the continuous variables among groups. The Bartlett test will be used to evaluate the homogeneity of variances. The Tukey Honest Significant Differences test will be used to perform the multiple comparisons. If the normality assumption or homogeneity of variances assumption is violated, the Kruskal-Wallis one-way ANOVA by ranks will be used. The Dunn test will be used to perform the multiple comparisons.

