Side Effects Rating Scale: 0 = No Change / 1 = Weak / 2 = Modest / 3 = Bothersome / 4 = Very Bothersome

	15 Minutes	30 Minutes	60 Minutes	90 Minutes	120 Minutes
Pain Score (0-10):					
	Side Effect Rating Scale Score (0 - 4)				
Fatigue					
Dizziness					
Nausea					
Headache					
Feeling of unreality					
Changes in hearing					
Changes in vision					
Mood changes					
Generalized discomfort					
Hallucination					
Rescue Analgesia Needed? (Y/N)					
Vital signs at 120 minutes or discharge	SBP:		HR:		RR:

Name of Provider Collecting Data

Signature of Provider Collecting Data

/

XIX. Appendix B

Hackensack Meridian Health
Hackensack University Medical Center Campus
 IV Medication Guidelines

**IV SUBANESTHETIC KETAMINE FOR ACUTE PAIN MANAGEMENT
 IN THE ADULT EMERGENCY and TRAUMA CENTER (ETC)**

SCOPE

- Patients under the care of the ETC may receive IV ketamine for the management of acute pain under the direct supervision of an attending physician
- Registered nurses in the ETC may administer IV ketamine for treatment of acute pain as an intermittent infusion in doses not to exceed those outlined in this guideline
- The use of IV ketamine for procedural sedation is outside of the scope of this guideline and is described elsewhere

INDICATIONS

- Ketamine can be used as single agent or as a part of a multi-modal pain regimen for the treatment of moderate or severe pain. Interest in ketamine has emerged as an alternative to opioid analgesics to reduce the overall exposure to opioids and potential for abuse.
- Sub-anesthetic doses of ketamine have demonstrated efficacy in the treatment of various pain types: abdominal, flank, back, musculoskeletal, complex regional pain syndrome, neuropathic and radicular pain, and sickle cell crisis

THERAPEUTIC CATEGORY

Anesthetic agent with analgesic properties

CLINICAL PHARMACOLOGY

Rapid acting anesthetic with analgesic properties associated with the endogenous release of catecholamines, which may elevate blood pressure and heart rate with minimal respiratory depression at analgesic doses.

MECHANISM OF ACTION

- Central and peripheral non-competitive antagonist of N-methyl-D-aspartate (NMDA) receptors
- Inhibits serotonin and dopamine reuptake and inhibits voltage-gated sodium and potassium channels

PHARMACOKINETICS

- Onset of action: 30 seconds
- Duration: Variable for analgesic effect (2-4 hours)
- Metabolism: Hepatic; metabolite: norketamine (25% activity of parent compound)
- Half-life: 2.5 hours

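### With no side-effect rating before dosing or during the infusion, symptoms already present cannot be separated from ketamine effects when the doses are compared

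*Combined protocol and SAP*

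**What the plan says.** Section I sets the secondary objective: "This study will also examine the frequency of adverse events secondary to ketamine", followed by a list of symptoms. Section VIII names the outcome as "incidence and severity of adverse drug events" and specifies SERSDA as the instrument. Section IX (Power and Sample Size) justifies 60 per group partly by the wish to learn more about safety before a larger study.

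The timing is given in three places:

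- Section VIII, narrative: "any adverse drug effects will be reassessed within 15 minutes from the end of the infusion and then every 30 minutes". Follow-up stops at 120 minutes, or at discharge if that comes first.
- Section VIII, Procedure list: "Treating resident or attending will reassess the patient at 15 minutes from the end of infusion, at 30 minutes from the end of infusion", then half-hourly to 120 minutes. The infusion itself lasts 20 minutes.
- Appendix A: side-effect columns at 15, 30, 60, 90 and 120 minutes only. Ten items are scored 0 to 4, with zero labelled as no change. Neither a reference time nor a recall period is given.

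Before dosing, Section VIII and Appendix A record vital signs and pain but no side-effect item. Section IX compares categorical variables by chi-square or Fisher's exact test and does not define a new or worsened side effect.

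**The concern.** Eligible patients have pain of at least 4/10, and the form lists abdominal, flank, sickle cell and trauma pain among the types. Several SERSDA items, such as nausea, fatigue, mood change and generalized discomfort, can belong to the presenting illness. A zero that means no change presupposes an earlier state, and that state is never recorded, so nobody can check afterwards whether a score of 1 or more was new. In its background section the protocol describes an adjunct-to-morphine trial that did take a baseline: "Adverse events were recorded and assessed at baseline and at each time point".

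Two results are at stake. The incidence in each arm, which this exploratory study is meant to supply for planning, may be too high. The difference between doses may be diluted, and a null comparison could then be read as equal tolerability.

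A second, weaker worry is that nothing is rated while the drug is running. Appendix B gives "Onset of action: 30 seconds", and Section II reports from the IV-push trial a significant "increase in the number of adverse events immediately after medication administration and at 15 minutes". A short-lived effect during the infusion could pass unrecorded.

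**Working it through.** **Plan's own figures.** The 60 per group has no calculation to reproduce. The 157 per group in Section IX concerns pain scores in a possible later trial. It reproduces exactly with pairwise two-sided t-tests at 0.05/3, a difference of 1.25, SD 3.4 and 80% power, and this point does not affect it.

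**Time of first rating.** The infusion takes 20 minutes. Under the narrative, the first rating is 0 to 15 minutes after it ends: 20 + 0 = 20 to 20 + 15 = 35 minutes from the start. Under the Procedure list it is 35 minutes.

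**Schedules side by side.** If the first rating is at 15 minutes, the narrative's half-hourly rule gives 15, 45, 75 and 105 minutes. The Procedure list and the form give 15, 30, 60, 90 and 120.

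**Effect of background symptoms.** The documents give no side-effect rates by dose, so the rates below are assumptions. Let p be the true drug-caused rate and b the share of patients in every arm who already have the symptom, independent of drug effect, and are scored as having it. The recorded rate is q = b + (1 − b)p, so q₂ − q₁ = (1 − b)(p₂ − p₁).

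Power for lowest versus highest dose, n = 60 per arm, two-sided 0.05, no multiplicity adjustment:

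power = Φ[(d − 1.96·SE₀)/SE₁], where d = q₂ − q₁, SE₀ = √(2q̄(1 − q̄)/n) and SE₁ = √([q₁(1 − q₁) + q₂(1 − q₂)]/n)

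- b = 0, 30% v 50%: SE₀ = 0.0894, SE₁ = 0.0876; (0.20 − 0.1753)/0.0876 = 0.28; power 61%.
- b = 20%, 44% v 60%: SE₀ = 0.0912, SE₁ = 0.0900; (0.16 − 0.1788)/0.0900 = −0.21; power 42%.

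| True rates | b | Recorded rates | Difference (points) | Power |
|---|---|---|---|---|
| 30% v 50% | 0 | 30% v 50% | 20 | 61% |
| 30% v 50% | 10% | 37% v 55% | 18 | 51% |
| 30% v 50% | 20% | 44% v 60% | 16 | 42% |
| 30% v 50% | 30% | 51% v 65% | 14 | 34% |
| 40% v 65% | 0 | 40% v 65% | 25 | 79% |
| 40% v 65% | 20% | 52% v 72% | 20 | 62% |

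**Effects missed during the infusion.** Let m be the share of affected patients whose effect has gone by the first rating and is not reported; the recorded rate is p(1 − m). With true rates of 30% and 50%:

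- m = 25% at both doses: 22.5% v 37.5%, a difference of 15 points.
- m = 50% at the low dose and 25% at the high dose: 0.30 × 0.50 = 15% v 0.50 × 0.75 = 37.5%, a difference of 22.5 points, more than the true 20.

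The recorded difference can shrink or grow, depending on how resolution varies with dose.

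**Has the drug effect gone by the first rating?** Using only the average half-life of 2.5 hours (150 minutes) in Section III, and ignoring distribution, the level 15 minutes after the infusion is 2^(−15/150) = 93% of its end-of-infusion value. The documents' own figures do not show that effects have resolved by then.

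**The case against.** A reader might infer that the schedule misses the period when ketamine effects peak. The documents do not support that. They give no peak time for a 20-minute infusion, and onset is neither peak nor offset. The trial with an excess immediately after dosing used IV push. The closer comparison, the infusion trial in older patients, is reported in Section II as showing an excess at 15 and 30 minutes, although the interval quoted for 30 minutes spans zero and the time origin is not stated. The narrative also permits a rating as the infusion ends, and with no recall period a patient may report earlier effects.

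A reader might also infer that presenting symptoms are counted as drug effects. That too goes further than the text. A rater who follows the zero anchor scores unchanged nausea as 0. Exclusions such as headache as chief complaint, altered mental status, psychiatric illness and an analgesic within four hours remove some background. Raters are blinded and the method is the same in every arm, so randomization should balance what remains.

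These limits stand, and so does the core of the point. An anchor that refers to an unrecorded state cannot be verified, and balance across arms prevents favouring one dose but does not prevent dilution. It is also fair that this is a secondary objective in a self-described exploratory study.

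**Conclusion.** The point holds in this form: there is no SERSDA rating before dosing, none is scheduled during the infusion, and new or worse is not defined, so symptoms already present cannot be separated from drug effects. If they are scored, dose differences shrink by (1 − b). Under the assumed 30% v 50% and b between 10% and 30%, the difference falls from 20 to between 18 and 14 points, and power from 61% to between 51% and 34%. This rests on assumed rates, a background equal across arms and independent of drug effect, and raters who do not fully apply the zero anchor. If they apply it perfectly, dilution from this source vanishes, but the data could not show that they did.

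That brief effects during the infusion may be lost is plausible. Its size, and the direction of any bias between doses, are not established. The point is worth correcting because it bears on a stated objective and the correction is small.

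**What to change.** 1. Appendix A: add a pre-dose SERSDA column, completed with the baseline vital signs.
2. Sections VIII and IX: define a side effect as a post-dose item score above that patient's pre-dose score, and compare doses on that. Keep the visit scores as the time course. A patient already at 4 on an item cannot worsen on it, so report how many there are.
3. State that the first post-infusion rating covers the time since the infusion began. A worst-since-start score could be added at that visit. It should be supportive only, because it asks for recall under a drug that Section III describes as amnestic.
4. Reconcile the assessment times in the Section VIII narrative with those in the Procedure list and the form.

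The cost is a short amendment, about one extra minute at baseline and some recall error. Visits, assessors and sample size do not change.

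Planned enrolment ended in January 2021 and this version is dated 4/20/2021, so many or all patients may already lack a pre-dose score. New columns cannot repair those records, and pooling them with later patients would mix two methods of ascertainment. Report patients without a pre-dose rating separately, state the limitation, and do not infer equal tolerability from a null result.
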